3. OBJECTIVES

3.1. Primary objective

• Efficacy: Incremental efficacy of a schedule with a fractional third dose at Month 2 over the standard schedule

To demonstrate the superiority of a 3-dose schedule of GSK Biologicals' malaria vaccine RTS,S/AS01_E with a fractional third dose at Month 2 compared to a standard schedule of RTS,S/AS01_E with three full doses in terms of vaccine efficacy against clinical malaria (primary case definition) over 12 months post-Dose 3.

Criterion:

The lower limit of the 95% confidence interval (CI) of the incremental vaccine efficacy estimate is above 0.

Refer to Section 5.1 for the definition of the primary endpoint.

3.2. Secondary objectives

Efficacy

- To assess the incremental vaccine efficacy against clinical malaria of a schedule with a fractional third dose at Month 2 versus a schedule with 3 full doses (primary and secondary case definitions) over 12 months post-Dose 3.
- To assess the incremental vaccine efficacy against clinical malaria, over 7 and
 12 months post-Dose 3, of a schedule with a fractional third dose at Month 7
 versus a schedule with a fractional third dose at Month 2.
- To assess the incremental vaccine efficacy against clinical malaria, over 7 and 12 months post-Dose 3, of a schedule with a fractional third dose at Month 7 versus a schedule with 3 full doses.
- To assess the incremental vaccine efficacy against clinical malaria, over 12 months post-Dose 4, post-Dose 5 and post-Dose 6 of a schedule with a fractional third dose at Month 2 and yearly fractional doses versus a schedule with full doses at Month 0, Month 1, Month 2 and yearly full doses.
- To assess the incremental vaccine efficacy against clinical malaria, over 12 months post-Dose 4, of a schedule with a fractional third dose at Month 7 versus a standard schedule with 4 full doses at 0,1,2,20 months.
- To assess the vaccine efficacy and impact of each RTS,S/AS01_E schedule over the entire study period by measuring the efficacy against clinical malaria at Months 14, 20, 26, 32, 38 and 50.
- To assess the prevalence of *P. falciparum* infections of each RTS,S/AS01_E schedule at cross-sectional visits (monthly from Month 0-20 and every three months thereafter till study end).

204889 (Malaria-094) Statistical Analysis Plan

 To assess the vaccine efficacy against incident *P. falciparum* infections defined by positive blood slide over the entire study period.

• Immunogenicity: Immune response to the CS and HBs antigens

- To describe the antibody response to the anti-circumsporozoite protein of P. falciparum (anti-CS) for each schedule.
- To describe the antibody response to the hepatitis B surface antigen (anti-HBs) for each schedule.

• Safety and reactogenicity

- To assess the safety of RTS,S/AS01_E for each schedule in terms of serious adverse events (SAEs), unsolicited adverse events (AEs) and AEs of specific interest.
- To assess the reactogenicity of RTS,S/AS01_E in terms of solicited local and general AEs.
- To assess the safety of RTS,S/AS01_E in terms of biochemistry (alanine aminotransferase [ALT], creatinine) and hematology (hemoglobin, white blood cells [WBC], platelets) parameters.

Refer to Section 5.2 for the definition of the secondary endpoints.

3.3. Tertiary objectives

Immunogenicity

To describe the anti-CS antibody response in terms of avidity.

Of note, blood samples taken in this study may also be used in ancillary studies. More details on ancillary studies are provided in the study design section of the protocol.

Refer to Section 5.3 for the definition of the tertiary endpoints.

4. CASE DEFINITIONS

Case definitions of Clinical Malaria

Primary case	P. falciparum asexual parasitemia > 5000 parasites/μl	
definition	AND presence of fever (axillary temperature ≥ 37.5°C) at the time of presentation	
	AND occurring in a child who is unwell and brought for treatment to a healthcare facility	
Secondary case	P. falciparum asexual parasitemia > 0	
definition	AND presence of fever (axillary temperature \geq 37.5°C) at the time of presentation or history of fever within 24 hours of presentation	
	AND occurring in a child who is unwell and brought for treatment to a healthcare facility	

Case definition of incident P. falciparum infection

Case definition 1	A documented P. falciparum asexual parasite density > 0 detected by blood slide reading at a
Case definition i	cross-sectional survey or as captured by the secondary case definition of clinical malaria (active
	detection of infection and passive case detection).

Case definition of prevalent P. falciparum infection

Case definition 1	A documented P. falciparum asexual parasite density > 0 detected by blood slide reading at a			
	cross-sectional survey (active detection of infection [ADI]).			

Table 1 Case definition of severe *P. falciparum* malaria

Adapted from [WHO, 2015].

P. falciparum parasitemia > 0 detected by microscopy and/or rapid diagnostic test (RDT)

AND one or more of the following, occurring in the absence of an identified alternative cause:

- Impaired consciousness: a Glasgow coma score < 11 in children two years of age or older (≥ 2 years) or a Blantyre coma score < 3 in children less than two years of age (< 2 years);
- Prostration: generalized weakness so that the person is unable to sit, stand or walk without assistance;
- Multiple convulsions: more than two episodes within 24h;
- Acidosis: a base deficit of > 8 mEq/l or, if not available, a plasma bicarbonate level of < 15 mmol/l or venous plasma lactate ≥ 5 mmol/l. Severe acidosis manifests clinically as respiratory distress (rapid, deep, labored breathing).
- Hypoglycemia: blood or plasma glucose < 2.2 mmol/l (< 40 mg/dl);
- Severe malarial anemia: hemoglobin concentration ≤ 5 g/dl or a hematocrit of ≤ 15% in children < 12 years of age with a parasite count > 10 000/µl;
- Renal impairment: plasma or serum creatinine > 265 µmol/l (3 mg/dl) or blood urea > 20 mmol/l;
- Jaundice: plasma or serum bilirubin > 50 μmol/l (3 mg/dl) with a parasite count > 100 000/μl;
- Pulmonary edema: radiologically confirmed or oxygen saturation < 92% on room air with a respiratory rate
 > 30/min, often with chest indrawing and crepitations on auscultation;
- Significant bleeding: including recurrent or prolonged bleeding from the nose, gums or venipuncture sites; hematemesis or melaena;
- Shock: compensated shock is defined as capillary refill ≥ 3 s or temperature gradient on leg (mid to proximal limb), but no hypotension. Decompensated shock is defined as systolic blood pressure < 70 mm Hg in children, with evidence of impaired perfusion (cool peripheries or prolonged capillary refill);
- Hyperparasitemia: P. falciparum parasitemia > 10% (i.e. percentage of infected red blood cells > 10%; corresponding to > 500 000/μl).

Table 2 Case definition of cerebral *P. falciparum* malaria

Adapted from [WHO, 2015].

Severe P. falciparum malaria with coma (Glasgow coma score < 11 in children two years of age or older [\geq 2 years] or Blantyre coma score < 3 in children less than two years of age [(< 2 years]);

AND

If malaria with seizure: coma persisting for > 30 min after the seizure.

Other treatable causes of coma should be excluded before diagnosing cerebral malaria (e.g. hypoglycaemia, bacterial meningitis).

5. ENDPOINTS

5.1. Primary endpoint

• Efficacy:

 The occurrence of clinical malaria meeting the primary case definition from Month 2.5 up to Month 14.

5.2. Secondary endpoints

• Efficacy:

- The occurrence of clinical malaria meeting the primary and secondary case definitions from Day 0 up to Month 50.
- The occurrence of incident *P. falciparum* infections from Day 0 to Month 50.
- The prevalence of *P. falciparum* infections defined by positive blood slide at each cross-sectional survey.
- **Immunogenicity**: Immune response to the CS and HBs antigens (immunogenicity subset)
 - Anti-HBs antibody concentrations, seropositivity and seroprotection measured before Dose 1, one month post-Dose 2 (group Fx017-20 only), before and one month post-Dose 3, before and one month after Dose 4, before and one month after each yearly dose and at study end (Month 50).
 - Anti-CS antibody concentrations and seropositivity measured before Dose 1, one month post-Dose 2 (group Fx017-20 only), before and one month post-Dose 3, before and one month after Dose 4, before and one month after each yearly dose and at study end (Month 50).

• Safety

- The occurrence of SAEs (all, fatal and related) during the whole study period according to the Medical Dictionary for Regulatory Activities (MedDRA) classification.

204889 (Malaria-094) Statistical Analysis Plan

- The occurrence of AEs and SAEs leading to withdrawal from further vaccination from Dose 1 (Day 0) up to Month 50, according to the MedDRA classification.
- The occurrence of severe malaria cases and cerebral malaria cases during the whole study period.
- The occurrence of potential immune-mediated diseases (pIMDs) from Day 0 up to Month 50, according to the MedDRA classification.
- The occurrence of meningitis from Day 0 up to Month 50, according to the MedDRA classification.
- The occurrence of seizures within 30 days (day of vaccination and 29 subsequent days) after each dose of study vaccine, according to the MedDRA classification.
- The occurrence of generalized convulsive seizure within seven days (day of vaccination and six subsequent days) after each dose of study vaccine, according to the Brighton collaboration guidelines [Bonhoeffer, 2004].
- The occurrence of unsolicited AEs within 30 days (day of vaccination and 29 subsequent days) after each dose of study vaccine, according to the MedDRA classification.
- The concentration of biochemistry (ALT, creatinine) and hematology (hemoglobin, WBC, platelets) parameters in the first 50 subjects (25 subjects per site) enrolled in each group (reactogenicity sub-cohort) before Dose 3, seven days post-Dose 3 and 30 days post-Dose 3.

• Reactogenicity (reactogenicity sub-cohort)

The occurrence of solicited local and general AEs in a the first 50 subjects enrolled in each group within four days (day of vaccination and three subsequent days) after Dose 3 of study vaccine (all groups including controls), after Dose 4 (groups R012-20, R012-14, Fx012-14 and Fx017-20), after Dose 5 (groups R012-14, Fx012-14 and Fx017-20) and after Dose 6 (groups R012-14 and Fx012-14).

5.3. Tertiary endpoints

Immunogenicity

Anti-CS antibody avidity at same time points specified in secondary endpoints

6. ANALYSIS SETS

6.1. Definition

Note that in order to align to International Committee on Harmonization (ICH) and Clinical Data Interchange Standards (CDISC) terminology the Total Vaccinated Cohort and the According To Protocol cohort have been renamed Exposed Set (ES) and Per-Protocol Set (PPS) respectively. A solicited safety set is an added set for tables including solicited data only.

6.1.1. All Enrolled Set

The enrolled set will include all subjects who signed informed consent.

6.1.2. Exposed Set (ES)

The ES will include all subjects who received at least one dose of study vaccine. The ES analysis will be performed per treatment actually administered.

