11.5. Cohorts for analyses

11.5.1. Total vaccinated cohort

The total vaccinated cohort (TVC) will include all subjects who received at least one dose of study vaccine. The TVC analysis will be performed per treatment actually administered.

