6.1.3. Per-Protocol Set for analysis of efficacy (PPS for efficacy)

For the primary analysis up to month 14, the PPS for efficacy will include all subjects from the ES who fulfilled eligibility criteria and who received all vaccinations according to protocol procedures within the protocol specified intervals that contribute to the time at risk in the follow-up period starting 14 days post-Dose 3.

For the final analysis up to month 50, all subjects who have not received Dose 4 of study vaccine or subsequent yearly doses (Dose 5 and Dose 6) according to protocol will be censored at the last contact date prior to the first missed dose recorded and will contribute to the PPS analysis up to censoring.

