6.2.2. Elimination from the PPS for analysis of efficacy and immunogenicity

A subject will be excluded from the PPS under the following conditions:

Code	Condition under which the code is used	Visit (timepoints) where the code is applicable	Applicable analysis set
800	Fraudulent data	All visits	immunology, efficacy
900	Invalid informed consent	All visits	immunology, efficacy
1030	Study vaccine not administered at all but subject number allocated Subject randomized but not vaccinated.	Visit 2, and onwards	immunology, efficacy
1040*	Administration of concomitant vaccine(s) forbidden in the protocol to be determined by CRDL from review of individual data listings	For efficacy set (3035 elimination code): a vaccine not foreseen by the study protocol administered during the period starting seven days before each dose and ending seven days after each dose of vaccine. It applies only for the three first doses.	immunology, efficacy
1050	Randomisation failure First vaccination not equal to the group the subject was randomized to. To be attributed by Statistician and CDR: check SBIR, replacement, vaccine administration	Time of randomization, and onwards	immunology, efficacy

C :	Statistical Analysis Pla		
Code	Condition under which the code is used	Visit (timepoints) where the code is applicable	Applicable analysis set
1070*	Vaccination not according to protocol: Incomplete vaccination course before treatment withdrawal Wrong replacement or study vaccine administered (not compatible with the vaccine regimen associated to the treatment number).	All visits were vaccinations are planned: • Control → Visit 2, 3 and 4 • R012-20 → Visit 2, 3, 4 and 24 • R012-14 → Visit 2, 3, 4, 18, 27 and 33 • Fx012-14 → Visit 2, 3, 4, 18, 27, and 33 • Fx017-20 → Visit 2, 3, 10, 24 and 30	immunology
1080*	Vaccine temperature deviation vaccine administered despite a Good Manufacturing Practices (GMP) no-go temperature deviation	For efficacy set (3075 elimination code): applies at the time of the first 3 doses. For control, R012-20, R012-14 and Fx012-14 at visit 2,3 and 4. For Fx017-20 at visit 2,3 and 7.	Immunology, efficacy
1090*	Expired vaccine administered	For efficacy set (3090 elimination code): applies at the time of the first 3 doses. For control, R012-20, R012-14 and Fx012-14 at visit 2,3 and 4. For Fx017-20 at visit 2,3 and 7.	Immunology, efficacy

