		vac6→ser10 (m50) is outside [+308-420 days]	
		• Fx017- 20:	
		vac2→ser2(M2) is outside [21-35 days]	
		vac3→ser4 (M8) is outside [21-35 days]	
		vac4→ser6 (M21) is outside [21- 35 days]	
		vac5→ser7 (M33) is outside [21- 35 days]	
		vac5→ser9 (M50) is outside [+476-616 days]	
2100	Serological results	All visits where serum samples are	Immunology
	not available post-	planned (see Table 1– time points for	
	vaccination if ALL are missing and subject in Immunogenicity	immunogenicity)	
2120	Subset	All vigits where some someles are	Immunalagy
2120	Incomplete assessment and mislabelling (sample	All visits where serum samples are planned (see Table 1– time points for immunog enicity)	Immunology
	tested/not tested) of		

Code	Condition under which the code is used	Visit (timepoints) where the code is applicable	Applicable analysis set
	blood sample, for specific assays		

Code	Condition under which the code is used	Visit (timepoints) where the code is applicable	Applicable analysis set
3100	Subjects without follow up data starting 14 days post dose 3 Note that subjects not receiving dose 4, 5 and 6 will be censored at the last contact prior to whichever first missed dose recorded	 Applies under following conditions: First 3 vaccinations are administered No data available 14 days after visit 4 for Control, R012-20, R012-14, Fx012-14 No data available 14 days after visit 10 for Fx017-20 	Efficacy
3200	Subjects not receiving first 3 doses	 Applies under following conditions For control, R012-20, R012-14, Fx012-14 → no vaccination administered at visit 2,3 and 4. For Fx017-20 → no vaccination administered at visit 2,3 and 10 	Efficacy

^{*}a Dynamic elimination approach will be used for the definition of the immunogenicity PPS (Analysis M21 E1_02, Analysis M33 E1_03, Final analysis). This means that for codes 1040, 1070, 1080,1090, 2080, only the data relevant/posterior to the deviation will be eliminated. For codes 2040, 2090, 2120, the data elimination will be visit specific. For the efficacy PPS subjects will be fully excluded based on the elimination codes. However, subjects included in the efficacy analysis could be censored at last contact date.

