7.3. Efficacy/Effectiveness

7.3.1. Analysis of efficacy planned in the protocol

The primary analysis of efficacy will be based on the PPS for efficacy. The effect of the vaccine will be characterized using different complementary standard methodologies.

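### The exposed set is grouped by treatment received for efficacy as well as safety, so no planned efficacy analysis keeps all vaccinated children in their randomised group

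*SAP*

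**What the plan says.** SAP 6.1.2 defines membership and grouping of the exposed set (ES): "The ES will include all subjects who received at least one dose of study vaccine", and "The ES analysis will be performed per treatment actually administered". Protocol 11.5.1 has the same rule under the older name: "The TVC analysis will be performed per treatment actually administered". Neither section makes an exception for efficacy.

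The primary analysis uses a different set. SAP 7.3.1 states that "The primary analysis of efficacy will be based on the PPS for efficacy", and SAP 6.1.3 builds that set from the ES: "the PPS for efficacy will include all subjects from the ES who fulfilled eligibility criteria" and were vaccinated according to protocol. The elimination codes in SAP 6.2.2 then remove, among others:

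- code 1030: "Subject randomized but not vaccinated" (also outside the ES, by SAP 6.2.1);
- code 1050: "First vaccination not equal to the group the subject was randomized to";
- code 3200: "Subjects not receiving first 3 doses".

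The ES carries the Day 0 to Month 14, 20, 26, 32, 38 and 50 efficacy and impact estimates, and the Day 0 to Month 14 comparison of Fx012-14 with R012-20 and R012-14 pooled (SAP 7.3.1.6 and Table 3; protocol 11.7.6).

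**The concern.** Grouping by treatment received is the usual choice for safety, because harm follows what was injected. For efficacy it lets an event after randomisation decide the arm, and the comparison is then no longer protected by randomisation for the children concerned.

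Two uses are at stake. The ES Day 0 to Month 14 comparison of fractional with full dose is the natural check on a per-protocol primary analysis, and it should not share that analysis's dependence on what was actually given. The longer ES analyses supply the impact figures and the efficacy of each schedule over the whole study. The Phase III efficacy over 48 months that the protocol cites as background (sections 1.1 and 1.3.2) came from an intention-to-treat cohort, so grouping by treatment received also weakens that comparison.

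**Working it through.** **Step 1: is there an as-randomised efficacy set anywhere?**

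| Set | Who is in it | Grouping stated | Efficacy analyses |
|---|---|---|---|
| All enrolled (SAP 6.1.1) | consent signed | none | none |
| ES / TVC (SAP 6.1.2, protocol 11.5.1) | at least one dose | treatment administered | all analyses from Day 0, and impact |
| Efficacy PPS (SAP 6.1.3, 6.2.2) | ES children eligible and vaccinated per protocol | none separate | primary, and the post-dose analyses |

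Intention to treat is mentioned only for the Phase III results. No set keeps all vaccinated children in their randomised group.

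**Step 2: which children does the rule move?** By protocol Table 23, the four RTS,S arms receive the same full doses at Months 0 and 1. At those visits only RTS,S and rabies vaccine can be told apart. From Dose 3 on, full and one-fifth doses also differ, but by protocol 7.3.1 both are drawn from the same two-dose vial presentation and differ only in the volume withdrawn.

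- *Wrong product at Dose 1.* Code 1050 removes the child from the PPS; the ES rule moves the child to another arm.
- *Other volume at Month 2.* In the ES the child crosses the primary contrast. Code 1050 looks only at the first vaccination. Code 1070, which covers a wrong study vaccine, is listed for immunology only and has no efficacy counterpart, although SAP 6.1.3 requires vaccination according to protocol. Whether this child stays in the efficacy PPS is therefore unclear.
- *Doses that fit no arm.* A Control child given RTS,S once, or an Fx017-20 child given a full volume at Month 7, matches no schedule. An Fx012-14 child given a full volume at Month 2 resembles both R012 arms, which SAP Table 3 analyses separately from Day 0 to Month 20 onward. The rule does not identify a group for these children.

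**Step 3: how large could it be?** The documents give no rate of such errors. The share m below is an assumption. Protocol 11.4 gives 0.29 episodes per person-year for full dose and 0.16 for fractional, so incremental efficacy is 1 − 0.16/0.29 = 44.8%. (Protocol 11.4 states 50%; the lower value implied by the rates is used here.) Suppose a share m of each arm receives the other arm's Dose 3 volume, unrelated to malaria risk. As-treated grouping still returns 44.8%. As-randomised grouping gives 1 − [(1−m)·0.16 + m·0.29] / [(1−m)·0.29 + m·0.16]:

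- m = 1%: 1 − 0.1613/0.2887 = 44.1%
- m = 2%: 1 − 0.1626/0.2874 = 43.4%
- m = 5%: 1 − 0.1665/0.2835 = 41.3%

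If errors are related to risk, the as-treated figure is biased as well, by an amount the documents cannot supply.

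**Step 4: is power an obstacle to grouping by randomised arm?** Start with the plan's own figure. Expected first events are n·(1 − exp(−rate·T)). With 500 and 250 evaluable children and T = 11.5/12 year this gives 121.3 + 35.5, about 156.9 events before rounding. Schoenfeld power at 2:1 is Φ(√(156.9 × 2/9) × |ln 0.552| − 1.96) = 94.0%, which agrees with the stated minimum of 90%. With all 600 and 300 enrolled children over the same window there are 188.2 events. Power is then 97.0% with no errors, 92.9% at m = 5% and 85.6% at m = 10%. A Wald variance with unequal event counts is less generous: 87.7% for the plan's own case, 92.7% for 600 versus 300, and 87.1% at m = 5%. Within each method, 600 versus 300 with up to 5% swapped stays close to the plan's own figure.

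**The case against.** The best defence is that the rule hardly ever bites. Randomisation and Dose 1 fall at the same visit (protocol Table 11), and the internet system issues a treatment number for each dose consistent with the allocated group (protocol 6.2.2.2). Apart from dosing errors, ES grouping and randomised grouping are identical. Children kept in the PPS had a first vaccine that agreed with their allocation. The Day 0 to Month 14 ES comparison is already planned, so only its grouping and label are in question. All of this stands, and it is why the point is a clarification. It does not justify the rule: the text applies to efficacy, and a pre-specified plan should not rely on an unwritten convention.

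A reader might go further and infer that a child who misses a dose is moved to another arm, for example that an R012-14 child without the Month 14 dose becomes an R012-20 child. The documents do not support this. Protocol 10.2.2 treats missed doses as an incomplete course of the child's own treatment, the protocol glossary ties treatment to the randomised allocation, and SAP Table 3 has no step that changes group at a missed dose. Nor could that example alter the Day 0 to Month 14 comparison, because the two R012 arms are pooled there and the Month 14 dose falls as the window closes.

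**Conclusion.** The gap is real and narrow. Taken literally, the plan regroups children given another arm's product or volume in every ES efficacy and impact analysis, and it leaves some of them without a group. The PPS removes misallocated and incompletely vaccinated children, so it does not fill the gap.

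The effect is probably small: at a 1% swap rate unrelated to risk, the two groupings differ by 0.7 percentage points (44.8% against 44.1%). That rests on an assumed error rate and on the sample-size incidences, which were set for the primary endpoint. A reader might infer that the efficacy results as a whole are seriously biased. The documents do not support that, since the rule differs from randomised grouping only for misdosed children. A bias range built on an assumed share of moved children and an assumed excess malaria rate would only reflect those assumptions, because the documents give neither.

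**What to change.** Reword SAP 6.1.2 and protocol 11.5.1 to: *ES efficacy and impact analyses are performed by randomised group; ES safety analyses are performed by treatment actually administered.* Name the planned ES Day 0 to Month 14 comparison of Fx012-14 with pooled R012, by randomised group, as the supportive analysis for the primary. Record the change in SAP section 10.

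The cost is one sentence in each document and a label on an existing analysis. The safety tables do not change. Children randomised but never vaccinated (code 1030) stay outside the ES, so this repairs the grouping but does not create a full intention-to-treat set. A count, by arm and dose, of children whose product or volume differed from allocation would show how much the choice mattered. The efficacy status of code 1070 should be reconciled with SAP 6.1.3 at the same time.
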